2. DATA SOURCES

Data for the study will be derived from the following sources:

Aetna

- Aetna Membership – The Membership table captures monthly membership along with current status (e.g., active, terminated, deceased). Several demographic and plan sponsor fields are included.
- Aetna Medical Case Database – Medical Case summarizes clinical events by linking or associating all of the claims submitted for a member during the same treatment event. The logic defines clinical events based on contiguous claims for five places of service (Inpatient Acute, Inpatient Non-Acute, Emergency Room, Facility-based Outpatient Procedure, and Non-Facility Outpatient Procedure). This supports identifying all costs related to one of these events. Important to this study, Medical Case logic assigns all claims linked to a case to one category of service—inpatient, ER, or outpatient facility.
- Aetna Claims Database – Claims data include diagnoses (ICD9-CM v1 and 10-CM); professional encounters (CPT); diagnoses and procedures rendered during inpatient, outpatient and covered skilled facility encounters (ICD9-CMv3 and ICD10-PCS); durable medical equipment (HCPCS); administered (HCPCS) and dispensed (NDC) pharmaceuticals; presence of laboratory, pathology and imaging services; and allowable costs of healthcare services. Hospital claims also include DRGs, which will not be used in this study. Claims for services not covered under a member's healthplan benefits may occasionally appear in the data (i.e. provider or member submitted claim which was subsequently denied), but not reliably, and will bear a cost of zero. Laboratory, pathology and imaging services performed in-hospital or ER may not consistently appear in claims.
- Episode Treatment and Episode Risk Groups – The Aetna data warehouse contains member-level episodes-of-care resource use and cost information (via the Optum Episode Treatment Group® utility) and retrospective risk adjustment and prospective predictive cost modeling (via Optum's Episode Risk Groups®).¹ The ETG software aggregates all medical and pharmacy services related to care for specified acute (distinct beginning and end) and chronic (one year of treatment) conditions.
- Aetna's Care Management (Case and Disease) Programs – Aetna's case management program identifies members with projected limited-term intensive care needs, and helps to coordinate care, referral to specialists and centers of excellence (where

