3. ANALYSIS OBJECTIVES

The analysis objectives corresponding to the study objectives listed in 1. INTRODUCTION AND BACKGROUND are the following:

Primary Analysis

1. Compare incidence of newly diagnosed atrial fibrillation (as defined by ≥ 30 seconds of atrial fibrillation or flutter detected by device, or a new clinical diagnosis recorded in claims data) at the end of the 4-month monitoring period in the immediate monitoring cohort (n=1,000) with delayed monitoring cohort (control group) (n=1,000) using ICD-9/ICD-10 codes.

Secondary Analyses

1. Compare time to first event of newly diagnosed atrial fibrillation (as defined by ≥ 30 seconds of atrial fibrillation or flutter detected by device, or a new clinical diagnosis recorded in claims data) at the end of the 4-month monitoring period in the immediate monitoring cohort (n=1,000) with delayed monitoring cohort (control group) (n=1,000) using ICD-9/ICD-10 codes.
2. Compare incidence of newly diagnosed atrial fibrillation (as defined by ≥ 30 seconds of atrial fibrillation or flutter detected by device, or a new clinical diagnosis recorded in claims data) at the end of the 4-month monitoring period in the immediate monitoring cohort (intervention group) (n=1,000) with delayed monitoring cohort (control group) (n=1,000) using HPD definition.
3. Compare prevalence of atrial fibrillation in the actively monitored cohort (n=2,000) with the matched observational control cohort (n=4,000) at 12 months.
4. Compare time to event of newly diagnosed atrial fibrillation in the actively monitored cohort (n=2,000) with the matched observational control cohort (n=4,000) at 12 months.
5. Compare the rate of initiation of anticoagulation therapy in the actively monitored cohort with the matched observational control cohort at 12 months.
6. Compare the rate of initiation of other atrial fibrillation-related therapies (antiarrhythmic agents excluding beta-blockers and calcium channel blockers, cardioversions, ablation procedures or hospitalizations with a primary diagnosis of AF) in the actively monitored cohort with the matched observational control cohort at 12 months.
7. Compare utilization in actively monitored cohort with the matched observational cohort at 12 months.
8. Compare time to first event of the combined endpoint of stroke, systemic embolism, or myocardial infarction in the actively monitored cohort with the matched observational control cohort at 3 years:

- a. In the entire cohorts.

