5. ENDPOINTS AND COVARIATES

[Data source in brackets]

Primary Endpoint

1. Atrial Fibrillation/Flutter: new diagnosis of atrial fibrillation or atrial flutter defined as:
 - a. ≥ 30 seconds of atrial fibrillation or flutter diagnosed and adjudicated on the iRhythm output (monitored cohort) [PI Diagnosis Database]
 - i. Date
 - ii. Duration
 - b. Claim for atrial fibrillation/atrial flutter with ICD-9 code 427.1 or 427.2 or ICD-10 code I48.91 or I48.9 [Aetna Claims Data; Aetna Medical Case]
 - i. Date

Secondary Endpoints

1. Atrial Fibrillation/Flutter: HPD algorithm [Aetna HPD Database]
2. Anticoagulation: Drug NDC codes for new refill for any:
 - a. Anticoagulant (dabigatran, rivaroxaban, apixaban) or
 - i. Date
 - b. P2Y12 Antagonists (clopidogrel, prasugrel or ticagrelor) without a new diagnosis of acute coronary syndrome
 - i. Date
4. Other AF-related therapies (i.e. antiarrhythmic agents excluding beta-blockers and calcium channel blockers, cardioversions, ablation procedures or hospitalizations with a primary diagnosis of AF)
5. UtilizationCommented [[name]]: Need to further define
3. Stroke-related visits during follow-up [Aetna Medical Case]
 - a. Inpatient
 - b. ER
 - c. Time to first stroke-related event (Inpatient or ER)
4. Myocardial infarction-related visits during follow-up [Aetna Medical Case]
 - a. Inpatient
 - b. ER
 - c. Time to first myocardial infarction-related event (Inpatient or ER)
5. Systemic thromboembolism-related visits during follow-up [Aetna Medical Case]
 - a. Inpatient
 - b. ER
 - c. Time to first systemic thromboembolism-related event (Inpatient or ER)
6. Death (Medicare population): [Aetna ATV; Aetna Membership Table]
 - a. Time to death (within 1 month of date)

- b. Cause of death
- 7. All-Cause Hospital Admissions [Aetna Medical Case]
 - a. Total number
 - b. Total length of stay
 - c. Individual admissions
 - i. Primary diagnosis
 - ii. Date
 - iii. Length of stay

Safety Endpoints

- 1. Hospital admission for primary bleeding diagnosis: [Aetna]
- 2. Incidence of non-AF, but other actionable heart rhythms captured by device (and confirmed by PI) [PI Diagnostic Database]
 - a. Atrial Tachycardia with variable block of > 30 seconds
 - b. Ventricular Tachycardia >5 beats
 - c. Pauses \geq 5 seconds
 - d. AV block
- 3. Early discontinuation of active monitoring in monitored cohort [Scripps Study Database]
 - a. Date of discontinuation
 - b. Cause of discontinuation

Exploratory Endpoint (Amiigo)

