- 1. Correlation between Amiigo-detected AF and Zio patch detected AF with rate of true and false positives during overlapping monitoring.

Other Endpoints

- 1. Followup Count of All-Cause ER Visits [Aetna Medical Case]
- 2. Followup Count of All-Cause IP Visits [Aetna Medical Case]
- 3. Followup Total Length of Stay for All-Cause IP Visits [Aetna Medical Case]
- 4. Followup Count of All All-Cause Visits (IP and ER) [Aetna Medical Case]
- 5. Followup Time to First All-Cause Event (IP or ER) [Aetna Medical Case]
- 6. Followup Count of Stroke-Related ER Visits [Aetna Medical Case]
- 7. Followup Count of Stroke-Related IP Visits [Aetna Medical Case]
- 8. Followup Total Length of Stay for Stroke-Related IP Visits [Aetna Medical Case]
- 9. Followup Count of All Stroke-Related Visits (IP and ER) [Aetna Medical Case]
- 10. Followup Time to First Stroke-Related Event (IP or ER) [Aetna Medical Case]
- 11. Followup Count of Systemic Embolic-Related ER Visits [Aetna Medical Case]
- 12. Followup Count of Systemic Embolic-Related IP Visits [Aetna Medical Case]
- 13. Followup Total Length of Stay for Systemic Embolic-Related IP Visits [Aetna Medical Case]

14. Followup Count of All Systemic Embolic-Related Visits (IP and ER) [Aetna Medical Case]
15. Followup Time to First Systemic Embolic-Related Event (IP or ER) [Aetna Medical Case]
16. Followup Count of Myocardial Infarction-Related ER Visits [Aetna Medical Case]
17. Followup Count of Myocardial Infarction-Related IP Visits [Aetna Medical Case]
18. Followup Total Length of Stay for Myocardial Infarction-Related IP Visits [Aetna Medical Case]
19. Followup Count of All Myocardial Infarction-Related Visits (IP and ER) [Aetna Medical Case]
20. Followup Time to First Myocardial Infarction-Related Event (IP or ER) [Aetna Medical Case]
21. Followup Diagnosis of Atrial Fibrillation [Aetna Claims Data]; [Aetna HPD]
22. Followup Mortality Aetna ATV; Aetna Membership Table
23. Followup Diagnosis of Alcoholism [Aetna HPD]
24. Followup Diagnosis of Benign Prostatic Hypertrophy [Aetna HPD]
25. Followup Diagnosis of Metastatic Cancer [Aetna Claims Data]
26. Followup Diagnosis of Cardiomyopathy [Aetna Claims Data]
27. Followup Diagnosis of Cataract [Aetna HPD]
28. Followup Diagnosis of Cerebrovascular Disorder [Aetna HPD]
29. Followup Diagnosis of Chronic Liver Disease [Aetna HPD]
30. Followup Diagnosis of COPD [Aetna HPD]
31. Followup Diagnosis of Chronic Renal Failure [Aetna HPD]

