40. Cardioversion [Aetna Claims Data]
41. Catheter Ablation [Aetna Claims Data]
42. Maze Procedure [Aetna Claims Data]
43. Left Atrial Appendage Occlusion Procedure [Aetna Claims Data]

44. Coronary Artery Bypass Grafting [Aetna Claims Data]
45. Cardiac Stent(s) [Aetna Claims Data]
46. Valve Surgery [Aetna Claims Data]
47. Percutaneous Valve Procedures (Transcatheter Aortic Valve Replacement/TAVR, Transcatheter Mitral Valve Repair) [Aetna Claims Data]
48. Cardiac Transplant [Aetna Claims Data]
49. Cardiac Resynchronization Therapy Device [Aetna Claims Data]
50. Left Ventricular Assist Device during Baseline [Aetna Claims Data]

Baseline Prescriptions:

51. Digoxin [Aetna Pharmacy]
52. Beta Blocker [Aetna Pharmacy]
53. Calcium Channel Blocker [Aetna Pharmacy]
54. Antiarrhythmic Drug [Aetna Pharmacy]
55. ACE Inhibitor or ARB [Aetna Pharmacy]
56. Loop Diuretic [Aetna Pharmacy]
57. Spironolactone [Aetna Pharmacy]
58. Eplerenone [Aetna Pharmacy]
59. Nitrates/Hydralazine [Aetna Pharmacy]
60. Entresto [Aetna Pharmacy]
61. Statin or PCSK9 [Aetna Pharmacy]
62. P2Y12 Receptor Inhibitor [Aetna Pharmacy]
63. Diabetes Medication [Aetna Pharmacy]

Baseline Utilization

64. Outpatient visit [Aetna Medical Case]

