The analysis will compare the proportion of subjects with newly diagnosed atrial fibrillation (numerator) per number of total number of subjects in group (denominator) during the first 12 months from the date of enrollment of the actively monitored subject between the actively monitored cohort and matched observational cohort using Fisher's exact test. Multivariable analysis of the AF/atrial flutter outcome will also be performed using binomial multivariable logistic regression models to include baseline demographic (age, sex, race/ethnicity, median household income, geography, insurance type), co-morbidity covariates. The same analysis will be performed for the other 12-month follow-up outcomes of new prescription for anticoagulation medication and new prescription of other AF-related medications. All analyses will be conducted first as intention-to-treat and second among the per-protocol population.

Matched Observational Cohort Study – 3 year Follow-up

Analyses at 3 years of follow up will focus on time to event for disease outcomes (stroke, myocardial infarction, and systemic thromboembolism) and hospitalizations (all-cause and for bleeding) compared between the actively monitored cohort and the matched observational control cohort after 3 years of follow-up. Bivariate time-to-event analysis will be conducted using Kaplan-Meier analysis with the time to event calculated from the date of the enrollment of the actively monitored subject and the date of the first event of the specific disease outcome (separate analysis for each outcome). Subjects not having an endpoint event during the observation period will be censored at the end of the 3-year follow-up or date of discontinued enrollment from Aetna. Multivariable analyses will be conducted using Cox proportional hazard models and will include potential confounders including age, sex, race/ethnicity, insurance type, variables related to geography and co-morbidity scores. For the Cox models, if assumptions of proportionality are not met (as assessed by Kaplan-Meier and plots of Schoenfeld residuals), models accounting for non-proportionality (using time*covariate interaction terms) will be run.

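### Baseline inpatient and ER use is not listed, matched on or named in any model, although hospitalisation and ER use are endpoints compared between volunteers and never-invited controls

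*SAP*

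**What the plan says.** **Endpoints.** SAP section 3 lists as secondary analysis 7 "Compare utilization in actively monitored cohort with the matched observational cohort at 12 months". Analyses 11 and 12 are time to first, and total number of, all-cause hospitalisations at 3 years. Section 5 lists "All-Cause Hospital Admissions [Aetna Medical Case" as a secondary endpoint, with number and length of stay. Under Other Endpoints it adds items such as "Followup Count of All-Cause ER Visits [Aetna Medical Case" and "Followup Count of All All-Cause Visits (IP and ER) [Aetna Medical Case". The Utilization entry itself is undefined and carries the comment "Need to further define".

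**Baseline.** The Baseline Utilization heading in section 5 has one entry: "64. Outpatient visit [Aetna Medical Case". The co-morbidity scores listed are CHA2DS2-VASc, the retrospective and prospective Episode Risk Groups, Charlson and Framingham.

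**Source.** SAP section 2 says Medical Case builds events from five places of service: "Inpatient Acute, Inpatient Non-Acute, Emergency Room, Facility-based Outpatient Procedure, and Non-Facility Outpatient Procedure".

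**Comparison groups.** SAP section 4 draws controls from eligible members who were never sent an invitation. They are matched on sex, year of birth and CHA2DS2-VASc score (exact, then within 1 point). Uptake among those approached is assumed to be 5%.

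**Models.** For the 3-year time-to-event analyses, including all-cause and bleeding hospitalisation, section 7 says the Cox models "will include potential confounders including age, sex, race/ethnicity, insurance type, variables related to geography and co-morbidity scores".

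**The concern.** A person's earlier hospital and ER use is the direct baseline value of these endpoints. The comparison is not randomised: one side answered an invitation, at an assumed rate of 1 in 20, and the other was never asked. Agreement on sex, birth year and CHA2DS2-VASc does not ensure agreement on prior hospital use. If volunteers had a different admission rate before enrolment and it persisted, part of that gap could be read as an effect of screening on hospitalisation. Its direction is not known in advance, since volunteers could be healthier or could be heavier users of care.

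The plan would also not reveal the gap. The match-balance comparison in SAP section 7 covers characteristics at enrolment, and prior inpatient and ER use is not among the listed covariates.

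**Working it through.** The documents state no rate, effect, standard deviation or power for utilization or hospitalisation, so there is no plan figure to reproduce. The check is a comparison of lists, followed by an illustration.

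**1. Baseline against follow-up (SAP section 5).**

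| Domain | Follow-up items | Baseline items |
|---|---|---|
| Diagnoses | 23-48 (26) | 14-39 (the same 26) |
| Prescriptions | 62-78 (17) | 51-63 (13; the four missing are anticoagulants) |
| Inpatient/ER use | 1-20 (counts, length of stay, time to first event) | none |
| Outpatient visit | none listed | 64 |

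The absence of baseline anticoagulants fits the exclusion of members on chronic anticoagulation. No similar reason explains the utilization rows. Item 64 may not even capture ordinary office visits, because the outpatient categories in Medical Case are procedures.

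**2. Where prior inpatient or ER use could enter the analysis.**
- Matching (SAP section 4): not a matching variable.
- 3-year Cox models (section 7): not named.
- 12-month logistic models (section 7): these cover AF, anticoagulants and other AF medications, not utilization or hospitalisation, so they do not bear on this point.
- Covariates added through the missing-data rule (section 6): the screen covers demographics and co-morbidity scores only.
- 12-month utilization (analysis 7) and 3-year total hospitalisations (analysis 12): no method, adjusted or unadjusted, is stated.

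**3. How large a residual imbalance would matter (assumptions, not document figures).** Take 2,000 monitored subjects and 4,000 controls (SAP section 7), two-sided alpha 0.05 and no true effect. Assume that 20-40% of controls are hospitalised by 3 years and that a hazard ratio HR remains from confounding.

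Events: D = 2,000 × [1 − (1 − p)^HR] + 4,000 × p.
z = √(D × 1/3 × 2/3) × |ln HR|.
Probability of a significant result = Φ(z − 1.96) + Φ(−z − 1.96).

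Example with p = 0.20 and HR = 0.90: D = 1,164, z = √(1,164 × 2/9) × 0.105 = 1.69, probability about 0.40.

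| Residual HR | p = 0.20 | p = 0.30 | p = 0.40 |
|---|---|---|---|
| 0.95 | 0.13 | 0.18 | 0.22 |
| 0.90 | 0.40 | 0.55 | 0.67 |
| 0.85 | 0.74 | 0.89 | 0.96 |

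The nominal value is 0.05.

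**4. What imbalance could produce such ratios (also assumed).** Let a share a of volunteers and c of controls have prior inpatient or ER use, and let that use multiply later use by R. The ratio between groups is [1 + a(R − 1)] / [1 + c(R − 1)].
- a = 10%, c = 15%: R = 2 gives 1.10/1.15 = 0.96; R = 3 gives 1.20/1.30 = 0.92.
- a = 15%, c = 25%: R = 2 gives 1.15/1.25 = 0.92; R = 3 gives 1.30/1.50 = 0.87.

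These ratios are before any adjustment for co-morbidity scores, which would be expected to move them towards 1.

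**The case against.** The strongest reply is that the plan already adjusts for much of this. The Cox models name co-morbidity scores. The listed scores include the Episode Risk Groups, which SAP section 2 describes as claims-based risk adjustment and cost prediction, so they probably carry part of prior resource use. The Cox covariate list is open-ended, so item 64 or other variables are not excluded. Protocol section 4 also names a propensity score for matching. Much of this stands for time to first hospitalisation and bleeding hospitalisation. It does not reach the count endpoints, which have no model. The propensity score gives little assurance, because its content is not stated and the SAP matching list omits it.

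A reader might draw three stronger conclusions, which the documents do not support:
- **That utilization is an inpatient/ER count.** The SAP leaves it undefined. The inpatient and ER counts sit under Other Endpoints and are not tied to analysis 7, which could yet include outpatient use.
- **That any prior difference passes in full into the results.** For the Cox analyses the co-morbidity scores make this too absolute.
- **That baseline adjustment would be worth 10-33% more subjects.** That range is 1/(1 − r²) − 1 with an assumed correlation of 0.3-0.5 in a linear model. It does not transfer to a Cox analysis. What counts is the correlation left after age and risk scores; at an assumed 0.15-0.3 the gain would be about 2-10%.

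**Conclusion.** The point holds as a gap in confounding control for secondary and safety analyses. Baseline inpatient and ER use is not listed, matched on or named in the Cox model, and the one baseline utilization item has no listed follow-up counterpart and is named in no model. For time to first all-cause hospitalisation and bleeding hospitalisation, confounding is probably reduced by the co-morbidity scores but not shown to be removed. For 12-month utilization and 3-year total hospitalisations the gap is wider, because no analysis is stated.

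The size of the residual bias cannot be derived from the documents. The illustration shows only that, at 2,000 against 4,000, a residual hazard ratio of 0.90-0.95 would raise the chance of a nominally significant result from 5% to between 13% and 67%. It rests on the assumed 20-40% event proportion. The randomised 4-month AF comparison is unaffected.

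**What to change.** - **SAP section 5:** keep item 64. Add baseline all-cause inpatient count, ER count and inpatient length of stay from Medical Case over a fixed pre-enrolment look-back (for example 12 months), allowing for baseline months of eligibility (covariate 10). Define Utilization.
- **SAP section 7, descriptive statistics:** tabulate these measures in the match-balance check.
- **SAP section 7, 3-year Cox models:** include the matching baseline measure for time to first all-cause hospitalisation and for bleeding hospitalisation.
- **Total hospitalisations and utilization counts:** specify a count model with follow-up enrolled time as offset, adjusted for the baseline count and the covariates already named for the Cox models.
- **Matching:** reconcile the protocol's propensity score with the SAP matching list.

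The cost is SAP wording and a pre-enrolment query of a database already used for these endpoints. The downside is that members with a short Aetna look-back contribute less baseline information.

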6. HANDLING OF MISSING DATA

Missing data will be quantified for all variables. Given that endpoints are based on claims data, endpoints that do not appear in the claims data are measured as zero or absent and are thus not considered missing during the time that the subject remains enrolled in Aetna. Medical and pharmacy coverage will be assessed to identify truly missing data from zero/absent. For time to event analyses, subjects are censored at time of disenrollment. In addition, age and sex were included in the inclusion criteria for all subjects, and thus are not anticipated to be missing. Patterns of missing-ness of other covariates will be assessed by determining bivariate associations of the missing data (have data/do not have data) with demographic variables and co-morbidity scores. Variables found to be significantly associated with missing data will be used as covariates in the multivariable models used for the primary and secondary endpoints.

7. STATISTICAL METHODOLOGY

Sample Size Determinations

For the 4-month RCT, the sample size of 1,000 subjects for each group (immediate monitoring = active monitoring and delayed monitoring=no active monitoring) achieves >99% power to find a difference between an expected incident atrial fibrillation rate of 5% in the active monitoring group and an expected incident atrial fibrillation rate of 0.5% group without active monitoring with a two-sided alpha of 0.05. This sample size also achieves adequate power for the detection of the difference between the two groups at lower event rates, achieving 98% power for an expected rate of 2% in the active monitoring group and 0.1% in the delayed monitoring group with a two-sided alpha of 0.05.

For the Matched Observational Cohort Study, at 12 months, sample sizes of 2,000 subjects in the active monitoring group (immediate monitoring + delayed monitoring) and 4,000 subjects in the matched control group achieves >99% power to find a difference in the expected atrial fibrillation rate of 7% in the active monitoring group and 2% in the matched control group with a two-sided alpha of 0.05.

For the Matched Observational Cohort Study, based on an expected prevalence of atrial fibrillation of 10% in both the actively monitored (i.e., n=200) and matched control cohorts (i.e, n=400), a 7.5% event rate/year in the matched observational cohort and a 50% reduction in events in the actively monitored cohort due to earlier diagnosis prior to having an event or symptom, the expected combined event rate is 5% in the actively monitored subjects and 12% in the matched observational controls. Given these assumptions, the sample size yields 81% power to detect the expected difference in time to event with a log rank test with a two-sided alpha of 0.05.

Descriptive Statistics

Descriptive statistics (frequency of categorical variables; means (or medians), standard deviations (or interquartile range), and ranges of continuous variables) will be calculated for all variables (endpoints and covariates for both the Randomized Controlled Trial and the Observational Follow-up Study). Distributions of all variables will be examined for outliers and normality (continuous variables) both graphically and by descriptive statistics. Descriptive statistics will also be calculated for the following sub-populations: 1) subjects included in the per-protocol analyses specified below; 2) subjects who receive a diagnosis of atrial fibrillation/atrial flutter by the end of 3 years; and 3) subjects enrolled in Medicare (for analysis

the combined endpoint that includes death). Bivariate analyses will be used to examine differences in subject characteristics at enrollment 1) by randomized group, to assess the effectiveness of randomization, and 2) by actively monitored vs. matched observational control cohort to assess effectiveness of matching. Bivariate associations will be assessed using statistical methods appropriate for the variable types (Fisher's exact for categorical variables; t-test, ANOVA or non-parametric equivalents for continuous variables).

Descriptive statistics for device usage will be calculated separately for immediate monitoring group and the delayed monitoring group for their respective active monitoring periods, starting at date of enrollment and ending with completion of monitoring with final patch.

Analysis of Randomized Controlled Trial

The primary analysis will compare the proportion of subjects newly diagnosed with atrial fibrillation (numerator) per number of total number of subjects in the randomized group (denominator) during the first 4 months of the study between the immediate monitoring (intervention group) and delayed monitoring (control) groups using Fisher's exact test. Multivariable analysis of the primary outcome will also be performed using binomial multivariable logistic regression models to include baseline demographic (age, sex, race/ethnicity, median household income, geography, insurance type), and co-morbidity covariates. The primary analysis will be conducted with the endpoint (AF/atrial flutter) defined by any event in the Aetna databases with the ICD-9/ICD-10 code for AF/atrial flutter. Secondary analysis will be conducted using the same methods with the AF/atrial flutter endpoint defined by the HPD.

Intention-to-treat analysis will include all subjects who were randomized to the immediate monitoring or delayed monitoring groups and follow-up for outcomes from the device and the Aetna databases will be from date of enrollment to time of completion of monitoring with final patch or 4 months following enrollment, whichever is longest.

A per-protocol analysis will also be performed which will be limited to subjects in the immediate monitoring group who has a Zio patch reading of a total of at least 30 minutes and all subjects randomized to the delayed monitoring group.

Analysis of Matched Observational Cohort Study—12 month Follow-up

Analyses for the Matched Observational Cohort Study will involve comparison of outcomes in the actively monitored group from the randomized controlled trial (intervention = exposure to Zio patch monitoring) and the matched controls. Analysis at 12-month follow-up will include

the outcomes of new atrial fibrillation diagnosis and new prescriptions for 1) anticoagulants and 2) other AF-related medications.

The analysis will compare the proportion of subjects with newly diagnosed atrial fibrillation (numerator) per number of total number of subjects in group (denominator) during the first 12 months from the date of enrollment of the actively monitored subject between the actively monitored cohort and matched observational cohort using Fisher's exact test. Multivariable analysis of the AF/atrial flutter outcome will also be performed using binomial multivariable logistic regression models to include baseline demographic (age, sex, race/ethnicity, median household income, geography, insurance type), co-morbidity covariates. The same analysis will be performed for the other 12-month follow-up outcomes of new prescription for anticoagulation medication and new prescription of other AF-related medications. All analyses will be conducted first as intention-to-treat and second among the per-protocol population.

Matched Observational Cohort Study – 3 year Follow-up

Analyses at 3 years of follow up will focus on time to event for disease outcomes (stroke, myocardial infarction, and systemic thromboembolism) and hospitalizations (all-cause and for bleeding) compared between the actively monitored cohort and the matched observational control cohort after 3 years of follow-up. Bivariate time-to-event analysis will be conducted using Kaplan-Meier analysis with the time to event calculated from the date of the enrollment of the actively monitored subject and the date of the first event of the specific disease outcome (separate analysis for each outcome). Subjects not having an endpoint event during the observation period will be censored at the end of the 3-year follow-up or date of discontinued enrollment from Aetna. Multivariable analyses will be conducted using Cox proportional hazard models and will include potential confounders including age, sex, race/ethnicity, insurance type, variables related to geography and co-morbidity scores. For the Cox models, if assumptions of proportionality are not met (as assessed by Kaplan-Meier and plots of Schoenfeld residuals), models accounting for non-proportionality (using time*covariate interaction terms) will be run.

We will use the same time to event analyses with 3 year follow-up to evaluate the same disease and hospitalization endpoints among the subset of subjects included in the matched observational cohort study who receive a diagnosis of atrial fibrillation during the study. All analyses will be performed as intention-to-treat with parallel exploratory analyses performed on per-protocol basis restricted to subjects enrolled in the monitoring group who underwent Zio patch monitoring.

Analysis of Safety Endpoints

For analysis of safety endpoints at 3 year follow-up, we will compare incidence of hospitalization for bleeding per person-years of follow-up between the actively monitored group and the matched observational control group. Hospitalizations for bleeding will also be characterized by length of stay. Other safety outcomes will be characterized for the period of active monitoring in the active monitoring group only. These include Incidence of non-AF, but other actionable heart rhythms captured by the Zio patch device, specifically: 1) Atrial Tachycardia with variable block of > 30 seconds; 2) Ventricular Tachycardia >5 beats; 3) Pauses \geq 5 seconds; and 4) AV block. We will also characterize early discontinuation of active monitoring in monitored cohort by cause and time to event.

